## 2.5. Sample size determination

A total of 520 participants are planned to be enrolled, with 65 participants per age subgroup in each of the 4 dose groups.

A non-evaluable rate of 23% and 30% in 18 to 64 years of age and  $\geq 65$  years of age groups, respectively yield an approximate sample size of 95 evaluable participants per dose group (i.e., 50 participants between 18 to 64 years of age and 45 participants above 65 years of age in each dose group), giving 77.8% overall power to fulfill the 2 SPR immunogenicity criteria in the first group that is 7.5 mcg antigen + AS03A (detailed further in [Section 3.1](#)). This assumes that the SPR is truly 20% higher than the critical value (namely 90% for participants 18 to 64 years of age and 80% for participants  $\geq 65$  years of age, respectively).

The statistical power in 7.5 mcg antigen + AS03A group will be 91.4% if the SPR is assumed as 85% in  $\geq 65$  years of age.

## 3. STUDY DESIGN

### 3.1. General Description

This is a phase I/II, observer-blind, randomized, age stratified, multi-center study in healthy adults of  $\geq 18$  years of age with four parallel groups, which will be conducted in the US. Participants will be randomly assigned to 4 study groups at Visit 1 (Day 1).

Each of these 4 groups will be stratified by age group to create 8 subgroups of equal size in each dose group: 18 to 64 years of age (approximately 50% of participants enrolled) and  $\geq 65$  years of age (approximately 50% of participants enrolled).

All analyses will be provided separately for each age group.

Each participant will receive 2 intramuscular dose of study vaccine 21 days apart. Each participant will participate for 6 months after receipt of the final dose administered.

- 375\_B group: Study intervention administration of 3.75  $\mu$ g and AS03B on Visit 1 (Day 1) and 21 days later
- 375\_A group: Study intervention administration of 3.75  $\mu$ g and AS03A on Visit 1 (Day 1) and 21 days later
- 750\_B group: Study intervention administration of 7.50  $\mu$ g and AS03B on Visit 1 (Day 1) and 21 days later
- 750\_A group: Study intervention administration of 7.50  $\mu$ g and AS03A on Visit 1 (Day 1) and 21 days later

---

Document: \\ieedc-vnasc01\BIOSdata\GSK\H5N8(Flu)\HAB99808\Biostatistics\Documentation\SAP\SAP\SAP v5.0\GSK H5N8-219833\_SAP\_v5.0\_19AUG2024.docx

Author: PPD

Version Number: 5.0

Version Date: 19AUG2024

Template No.: CS\_TP\_BS016 Revision 7

Reference: CS\_WI\_BS005

Effective Date: 01Nov2021

later

Table A Study Groups

Study groups	Number of participants	Age (years of age)	Study interventions
375_B	65	18 to 64	3.75 µg and AS03B
375_B	65	≥ 65	3.75 µg and AS03B
375_A	65	18 to 64	3.75 µg and AS03A
375_A	65	≥ 65	3.75 µg and AS03A
750_B	65	18 to 64	7.50 µg and AS03B
750_B	65	≥ 65	7.50 µg and AS03B
750_A	65	18 to 64	7.50 µg and AS03A
750_A	65	≥ 65	7.50 µg and AS03A

All the participants will have screening laboratory tests to determine eligibility for the study. The first 50% of enrolled participants in each age and dose group will be required to have onsite visits for safety laboratory tests 7 days after each vaccination (i.e., Visit 2 and Visit 4). All other participants will have a remote visit (e.g., telephone call, video call, email, or text communication) with the site.

---

Document: \\ieedc-vnasc01\BIOSdata\GSK\H5N8(Flu)\HAB99808\Biostatistics\Documentation\SAP\SAP\SAP v5.0\GSK H5N8-219833\_SAP\_v5.0\_19AUG2024.docx

[figure not shown]
Author: PPD Version Number: 5.0  
 Version Date: 19AUG2024

Template No.: CS\_TP\_BS016 Revision 7

Reference: CS\_WI\_BS005

Effective Date: 01Nov2021

Figure A: Study Schema

\* Visit 2 and Visit 4 → First 50% participants in each dose and age group will be site visit for safety lab draw; the remaining 50% will have Remote Visit.  
 \*\* Only SAEs related to study participation will be collected between Screening and Visit 1.

There could be additional unscheduled or ad-hoc visit for repeat safety lab draws if indicated between Visits 2 and 3; Visits 4 and 5

Abbreviations: AE=adverse event; EOS=end of study; immuno=immunogenicity blood draw; iSRC=internal safety review committee; MAE=medically attended adverse event; pIMD=potential immune-mediated disease; SAE=serious adverse event.

### 3.2. Schedule of Events

Schedule of events can be found in Section 1.3 of the protocol. Refer also to [Table B.](#)

---

Document: \\ieedc-vnasc01\BIOSdata\GSK\H5N8(Flu)\HAB99808\Biostatistics\Documentation\SAP\SAP\SAP v5.0\GSK H5N8-219833\_SAP\_v5.0\_19AUG2024.docx  
 Author: PPD Version Number: 5.0  
 Version Date: 19AUG2024

Template No.: CS\_TP\_BS016 Revision 7

Reference: CS\_WI\_BS005

Effective Date: 01Nov2021

### **3.3. Changes to Analysis from Protocol**

No changes.

## **4. PLANNED ANALYSES**

The following analyses will be performed for this study:

- Analyses for Safety Review Team (SRT) and Internal Safety Review Committee (iSRC) review
- Interim Safety Analysis at Day 43
- Interim Immunogenicity Analysis at Day 43
- Final Analysis

All planned analyses identified in this SAP will be performed by IQVIA Biostatistics following Sponsor Authorization of this SAP, Database Lock and Sponsor Authorization of Analysis Sets.

Unblinded summaries for the iSRC will be performed by a separate IQVIA team.

### **4.1. SRT and iSRC Reviews**

#### **SRT Review**

The SRT is responsible for ongoing safety monitoring and will monitor cumulative, blinded safety data (including serious and non-serious AEs).

#### **iSRC Review**

The iSRC is a review body internal to GSK but external to the vaccine project who will review unblinded data at the planned safety reviews of the first 50 participants upon reaching 7 days post dose 1 and also upon reaching 7 days post dose 2.

Enrollment will be capped to 20 participants per day until the iSRC reviews have been completed. Following iSRC recommendation, the enrollment will be opened with no limitations.

Further details on the iSRC will be included in a separate iSRC charter

---

Document: \\ieedc-vnasc01\BIOSdata\GSK\H5N8(Flu)\HAB99808\Biostatistics\Documentation\SAP\SAP\SAP\SAP v5.0\GSK H5N8-219833\_SAP\_v5.0\_19AUG2024.docx

Author: PPD Version Number: 5.0

Version Date: 19AUG2024

Template No.: CS\_TP\_BS016 Revision 7

Reference: CS\_WI\_BS005

Effective Date: 01Nov2021

## 4.2. Interim Analysis

The interim analysis, including reactogenicity, safety and immunogenicity data, is planned when data collected through to, and including, the Day 43 visit, is available for all participants.

### 4.2.1. Interim Safety Analysis at Day 43

An analysis will be performed on data collected through the Day 43 visit. Elements will include:

- Analyses of cleaned solicited administration site events and solicited systemic events data collected during a 7-day follow-up period (i.e., day of vaccination and 6 subsequent days) after each vaccination.
- Analyses of unsolicited AEs reported up to the Day 43 visit (i.e., day of vaccination and 20 subsequent days after each vaccine) and cleaned in so far as is possible, will be carried out.
- Analyses of SAEs, pIMDs, MAEs, pregnancies, and withdrawals due to AEs, collected up to the Day 43 visit, will be carried out.
- No study report will be prepared. Access to individual treatment codes will be restricted to the designated statisticians in charge of the analysis. No individual listings or data with the participants' identifying information will be disseminated. Listings of final data will be provided with the EOS report.

### 4.2.2. Interim Immunogenicity Analysis at Day 43

An analysis will be performed on data collected through the Day 43 visit. Elements will include:

- Analyses of cleaned immunogenicity data, for analysis of vaccine-homologous HI antibody titers and MN titers, collected through the Day 43 visit will be conducted.
- Results will be presented in a Day 43 statistical report. Access to individual treatment codes will be restricted to the designated statisticians in charge of the analysis. No individual listings or data with the participants' identifying information will be disseminated. Listings of final data will be provided with the EOS report.

All analyses will be performed on data that has been cleaned and locked. The possibility of post-analysis changes to data evaluated at Day 43 exists, since data collection and data entry may continue through 6 months post dose 2. All final data will be presented in the listings provided at 6 months post dose 2.

---

Document: \\ieedc-vnasc01\BIOSdata\GSK\H5N8(Flu)\HAB99808\Biostatistics\Documentation\SAP\SAP\SAP v5.0\GSK H5N8-219833\_SAP\_v5.0\_19AUG2024.docx

Author: PPD Version Number: 5.0

Version Date: 19AUG2024

Template No.: CS\_TP\_BS016 Revision 7

Reference: CS\_WI\_BS005

Effective Date: 01Nov2021

## 4.3. Final Analysis

The final analysis includes all data obtained until 6 months post-last dose (end of study [EOS]) and includes safety summaries along with immunogenicity endpoints summaries.

This SAP is focused / limited to planned interim and final analyses. Outputs required for the interim analyses will be flagged in the tables, figures and listings (TFL) mock shells document.

## 5. ANALYSIS SETS

Agreement and authorization of participant data included/excluded from each analysis set and rules for excluding data requiring knowledge of unblinded data will be obtained prior to the unblinding of the study.

### 5.1. Process for Analysis Set Assignment

- Prior to database lock, a transfer of raw data from the electronic Case Report Form (eCRF) will occur, and participants will be assigned to analysis sets in accordance with the definitions in this SAP and the available data at that time. However, protocol deviations will be monitored continuously throughout the study.
- Listings for participants excluded from each final analysis set and reasons for exclusion will be prepared for sponsor review ahead of database lock in order to allow appropriate related data queries to be issued.
- A Data Review meeting will be held to confirm analysis set assignment, along with protocol deviations review (see protocol deviations management plan [PDMP], to include details of which protocol deviations (PDs) lead to exclusion from per protocol analyses), for each participant and any changes will be recorded. Changes will be implemented, and an updated analysis set assignment will be approved by the sponsor.
- Sponsor authorization of the analysis sets will be necessary prior to database lock. Once approved, analysis sets will be finalized, and the database will be locked.
- After database lock, the final analysis sets will be derived using the final study data, i.e., clinical database (eCRF), external vendor data (immunogenicity results) and protocol deviations log.

### 5.2. Screened Set [SCR]

All participants who were screened for eligibility.

---

Document: \\ieedc-vnasc01\BIOSdata\GSK\H5N8(Flu)\HAB99808\Biostatistics\Documentation\SAP\SAP\SAP\SAP v5.0\GSK H5N8-219833\_SAP\_v5.0\_19AUG2024.docx  
Author: PPD Version Number: 5.0  
Version Date: 19AUG2024

Template No.: CS\_TP\_BS016 Revision 7

Reference: CS\_WI\_BS005

Effective Date: 01Nov2021

### **5.3. Enrolled Set [ENR]**

All participants who were randomized, received study intervention or had immunogenicity blood sample. For analyses and displays based on ENR, participants will not be presented by study group.

### **5.4. Exposed Set [ES]**

Participants who received a study intervention. For analyses and displays based on ES, participants will be classified according to study intervention administered at dose 1 (i.e., study intervention actually received).

### **5.5. Diary Set [DS]**

Participants who received a study intervention and provided information (at least one AE for at least one day) on any solicited AE. For analyses and displays based on DS, participants will be classified according to study intervention administered at dose 1 (i.e., study intervention actually received). Participants to have at least one day of complete diary data to be included in DS.

### **5.6. Per Protocol Set [PPS]**

All eligible participants who received the 2 doses of study intervention as per-protocol, had Day 1 and post dose anti-HI immunogenicity results on Day 43 as per blood draw interval at Day 43.

In addition, participant data at a specific blood draw visit will be excluded from the PPS when:

- Results from a blood sample deviated from blood draw intervals (refer to protocol Table 1)
- Results from a blood sample occurred after intercurrent conditions that may interfere with immunogenicity (i.e., malignancy, immunosuppressive or immunodeficient conditions) or after a prohibited concomitant medication/vaccination.

Critical data missed or eliminated from PPS among participants in the ES will be classified as important protocol deviations.

---

Document: \\ieedc-vnasc01\BIOSdata\GSK\H5N8(Flu)\HAB99808\Biostatistics\Documentation\SAP\SAP\SAP v5.0\GSK H5N8-219833\_SAP\_v5.0\_19AUG2024.docx

Author: PPD Version Number: 5.0

Version Date: 19AUG2024

Template No.: CS\_TP\_BS016 Revision 7

Reference: CS\_WI\_BS005

Effective Date: 01Nov2021

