5.2.2 Prior/Concomitant Therapy

13. Use of any investigational or non-registered product (drug, vaccine, or medical device) other than the study vaccine during the period beginning 30 days before the first dose of study vaccine (Day -29 to Day 1), or planned use during the entire study period.
14. Use of public health emergency vaccines like COVID-19, Monkey pox (mpox) etc. These can be given at any time, but there should a gap of 2 weeks before a dose of study vaccine can be given.
15. Use of any licensed vaccines: prior to receipt of the study vaccine (2 weeks for inactivated vaccines and 4 weeks for live vaccines) and continuing up to 3 weeks after receiving the dose 2 of study vaccine.
16. Administration of long-acting immune-modifying drugs at any time during the study period (e.g., infliximab).
17. Administration of immunoglobulins and/or any blood products or plasma derivatives during the period starting 3 months before the first dose of study vaccine or planned administration during the study period.
18. Chronic administration (defined as more than 14 days in total) of immunosuppressants or other immune-modifying drugs during the period starting 3 months prior to the first vaccine dose and through the entire study period. For corticosteroids, this will mean prednisone equivalent ≥ 20 mg/day for 14 days or a total of ≥ 280 mg of prednisone equivalent dose in any 14-day period. Inhaled and topical steroids are allowed.

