5.4 Criteria for Temporarily Delaying Enrollment and Vaccination

Vaccination may be postponed within the allowed time interval ([Table 2](#)) until transient circumstances cited below have been resolved:

- Acute disease and/or fever at the time of each vaccination: Fever is defined as a temperature of or above 38.0°C/100.4°F. The preferred route for measuring temperature in this study will be oral. Participants with a minor illness (such as mild diarrhea, mild upper respiratory infection) without fever may be enrolled at the discretion of the investigator.
- Use of antipyretics/analgesics (e.g., acetaminophen and non-steroidal anti-inflammatory drugs [NSAIDs]) and/or antibiotics within 3 days prior to vaccination. Low-dose aspirin (81 mg daily) regimen is permitted.
- Use of public health emergency vaccines like COVID-19, Monkey pox etc. These can be given at any time, but there should a gap of 2 weeks before a dose of study vaccine can be given.

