6.8 Concomitant Therapy

Any medication or vaccine (including over-the-counter or prescription medicines, recreational drugs, vitamins, and/or herbal supplements) or other specific categories of interest that the participant is receiving at the time of enrollment or receives during the study must be recorded along with:

- Reason for use
- Dates of administration including start and end dates
- Dosage information including dose and frequency
- Route of administration
- For vaccines (if applicable) include brand name and manufacturer (plus lot number if available)

Concomitant therapy that meets the exclusionary criteria for this study is listed in Section [5.2.2](#).

The medical monitor should be contacted if there are any questions regarding concomitant or prior therapy.

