9.3 Analysis Sets

Table 9 Analysis Sets

Analysis Set	Description	Analyses Evaluated
Screened	All participants who were screened for eligibility.	Study Population
Enrolled (ENR)	All participants who were randomized, received study intervention or had immunogenicity blood sample.	Study Population
Exposed Set (ES)	Participants who received a study intervention. Participants will be analyzed according to the study intervention administered at dose 1.	Safety (unsolicited AE, number of participants with changes in laboratory toxicity grading from baseline, SAE, pIMD, MAE)
Diary Set (DS)	Participants who received a study intervention and provided information on solicited AEs. Participants will be analyzed according to the study intervention administered at dose 1.	Solicited AE
Per Protocol Set (PPS)	
All eligible participants who received the 2 doses of study intervention as per protocol, had Day 1 and Day 43 post dose anti-HI immunogenicity results as per blood draw interval at Day 43.
 
In addition, participant data at a specific blood draw visit will be excluded from the PPS when:
 
 • Results from a serological blood sample deviated from blood draw intervals (refer to Table 2) • Results from a serological blood sample occurred after intercurrent conditions that may interfere with immunogenicity (i.e., immunosuppressive, immunodeficient conditions, or malignancy) or after a prohibited concomitant medication/vaccination 
The analysis will be done according to the treatment that participants received at Visit 1.
	
Efficacy
 
The PPS will be used for the immunogenicity analyses.

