9.3.1 Criteria for Elimination from Analysis

All conditions leading to full or partial data elimination of a participant for the per protocol set (PPS) analysis will be classified as major protocol deviations. These conditions are already mentioned in the PPS definition and will be further detailed in the SAP and the Study Deviation Rules document which will be finalized prior to the interim analysis defined in Section 9.5.

Key major deviations include, but are not limited to, the following:

- Participants enrolled who did not meet eligibility criteria
- Participants incorrectly vaccinated
- Participants who did not receive study vaccinations as planned in protocol
- Participants who did not have serological blood draws as planned in protocol
- Participants with a blood draw outside of allowed time window
- Participants with a vaccination done outside of allowed time window. These key major deviations will be assessed based on the data collected in the eCRFs.
- Occurrence of immunosuppressive or immunodeficient conditions before a blood draw visit.

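### Should Day 43 samples drawn after a permitted non-study vaccine be taken out of the per protocol set, or analysed separately?

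*SAP*

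**What the plan says.** Protocol 9.3 (Table 9) and SAP 5.6 give the same sample-level rule. A result leaves the PPS if the draw was out of window, if it followed an interfering condition, or if it came "after a prohibited concomitant medication/vaccination". SAP 5.6 words the last two grounds as malignancy, "immunosuppressive or immunodeficient conditions) or after a prohibited concomitant medication/vaccination". The primary estimand in SAP 2.4 lists prohibited medication and intercurrent medical conditions as intercurrent events and refers back to SAP 5.6.

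Neither document defines *prohibited* further. The nearest pointer is Protocol 6.8: "Concomitant therapy that meets the exclusionary criteria for this study is listed in Section" 5.2.2. Two criteria there matter:

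- Criterion 15 restricts licensed vaccines before the study vaccine and "continuing up to 3 weeks after receiving the dose 2 of study vaccine".
- Criterion 14 covers emergency vaccines such as COVID-19 and mpox: "These can be given at any time, but there should a gap of 2 weeks" before a study dose. Protocol 5.4 repeats the allowance.

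The Visit 5 draw may be 14-35 days after dose 2 (Protocol Table 2, SAP Table B); the upper limit was 28 days before Amendment 3.0. On elimination rules, Protocol 9.3.1 adds: "These conditions are already mentioned in the PPS definition and will be further detailed in the SAP and the Study Deviation Rules document". SAP 5.1 leaves the list of deviations that exclude a participant from per protocol analyses to the protocol deviations management plan (PDMP).

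**The concern.** The restriction on licensed vaccines ends on day 21 after dose 2, and the draw may come as late as day 35. A vaccine on day 20 removes the later sample; a vaccine on day 22 does not, although it is closer to the draw. Amendment 3.0 lengthened the draw window by a week and left criterion 15 at 3 weeks. Emergency vaccines have no stated limit at all between dose 2 and the draw.

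None of the planned analyses selects on an intervening vaccine. The 14-28 day sensitivity analysis in SAP 15 selects on visit timing, and the conditional analysis on the exposed set removes no samples for this reason.

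Success depends on the lower confidence limit for the seroprotection rate (SPR) in the PPS, and the first dose group gates the hierarchy. If another vaccine lifted some titers over 1:40, a group could pass that should not. With about 50 and 45 evaluable participants per age group, a borderline result can turn on one person.

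**Working it through.** **Planned power.** Inputs from Protocol 9.2 and SAP 2.5: n = 50 (18-64 years) with true SPR 90% and limit 70%; n = 45 (65 years and older) with true SPR 80% and limit 60%. With two-sided 95% Clopper-Pearson intervals, the smallest passing counts are 42/50 (lower limit 70.9%) and 34/45 (60.5%). Exact binomial power is 0.9421 and 0.8259. The product is 0.778, the plan's 77.8%.

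**Width of the gap for licensed vaccines.** The longest interval from a permitted vaccine to the draw depends on whether day 21 itself is restricted:

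| First permitted day | Draw on day 35 | Draw on day 28 |
|---|---|---|
| Day 22 | 35 - 22 = 13 days | 28 - 22 = 6 days |
| Day 21 | 35 - 21 = 14 days | 28 - 21 = 7 days |

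For the planned draw on day 21, no permitted licensed vaccine comes on an earlier day after dose 2.

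**What the 14-28 day analysis removes.** Count pairs of a permitted vaccine day and a strictly later draw day d. With day 22 as the first permitted day, the sum of (d - 22) for d = 22 to 35 is 91, and for d = 22 to 28 it is 21. The analysis drops 91 - 21 = 70. With day 21 permitted the counts are 105 and 28, so 77 are dropped. These are day pairs, not expected numbers of participants.

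**Emergency vaccines between doses.** The 2-week gap before dose 2 plus a draw at least 14 days after it puts such a vaccine at least 14 + 14 = 28 days before the draw. The open interval is the one after dose 2.

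**What removing samples would show.** In the older group, 34/45 passes, while 33/44 has a lower limit of 59.7% and fails. At the planned rate, P(34 of 45) = 0.1054, and 0.1054 / 0.8259 = 12.8% of passing results in that age group. Deleting one seroprotected sample would turn these into fails. Deleting one sample at random, with no vaccine effect at all, would do so in 12.8% x 34/45 = 9.6%. Deleting a sample below 1:40 raises the limit instead (34/44: 62.2%). The flips thus measure lost sample size, not contamination.

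The rerun would also be weaker. With 1, 2, 3, 4 or 5 fewer samples per age group, joint power is 70.8%, 69.2%, 72.1%, 64.5% or 67.6% (not monotone, because counts are discrete).

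**What contamination would take.** The documents give no rate and no effect, so this is purely an assumption. Let f be the share exposed and c the share of exposed participants otherwise below 1:40 who cross it. At the null boundary the observed rate is 0.70 + 0.30fc or 0.60 + 0.40fc. The chance of passing in each age group is:

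| f | c | 18-64 years | 65 and older |
|---|---|---|---|
| 0 | any | 1.83% | 2.16% |
| 2% | 0.5 | 2.03% | 2.45% |
| 5% | 0.5 | 2.38% | 2.95% |
| 10% | 0.5 | 3.08% | 3.98% |
| 10% | 1 | 5.03% | 6.93% |

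The nominal 2.5% is clearly exceeded only if exposure is fairly common and an unrelated vaccine moves a large share of non-responders over the H5N8 threshold. Nothing in the documents supports either condition.

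**The case for a change.** The best argument for a change is consistency. The plan already accepts that a prohibited vaccination spoils a sample, so a calendar cut-off that ends before the draw does not follow its own logic. Late visits are documented: the window was widened because many participants fell outside it. A flag, a count and a rerun of existing tables would cost little, and a count of zero would close the question.

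Part of this stands. The protocol and SAP do not say outright how such a sample is handled, and 5.2.2 as the meaning of *prohibited* is an inference. Criteria 14 and 15 can be read as a specific allowance beside a general rule, though the text does not say so; how they fit together and with the draw window is for the sponsor to state. The 14-28 day analysis keeps draws on days 22-28, and for emergency vaccines it removes late draws only incidentally.

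The rest does not carry a change. Excluding only prohibited vaccination is a coherent estimand choice, and a permitted vaccine is by design not an intercurrent event. The rerun would leave the primary set and the success test alone, and it could not separate a vaccine effect from lost precision.

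**Conclusion.** No change to the plan. The window mismatch exists: up to 13 or 14 days for licensed vaccines, depending on how day 21 is read, and the whole interval from dose 2 to the draw for emergency vaccines. It is a gap that the analysts can fill sensibly. Protocol 9.3.1 and SAP 5.1 place the detailed elimination rules in the Study Deviation Rules document and the PDMP, with a data review meeting before lock. Protocol 6.8 records "Dates of administration including start and end dates" for every vaccine, and SAP 12 and 6.1 list vaccinations with study day. Affected samples can therefore be found and mentioned if there are any.

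This conclusion rests on three points. No statement in either document says that a non-study vaccine changes H5N8 HI titers. No figure is given for how often one is received between dose 2 and the draw. The two deviation documents were not available and may already hold a rule. Evidence of frequent exposure together with a real cross-effect on titers would reopen the question. On the documents as they stand, the effect may be nil, and an added analysis would not alter the formal result.
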